6.6 Missing Data Handling and Analysis Method

If there are any missing or incomplete data, they shall be handled as shown below.

- If there is any missing value in the demographic data, it shall not be replaced and shall be analyzed as it is.
- For the Mayo score for the evaluation of the clinical response, clinical remission, and mucosal healing among the effectiveness endpoints, if a missing value occurs at a certain point, it shall be handled as shown below.
 - If a missing value occurs at the partial Mayo score (stool frequency, rectal bleeding, physician's
 global assessment), the most recently obtained value shall be analyzed as if it were obtained at the
 time (LOCF method).
 - If a missing value occurs at the endoscopic findings subscore in the full Mayo score, it shall not be replaced and shall be analyzed as it is.
- Among the continuous data used in the analysis, the data that include a sign of inequality, symbols, etc. (e.g., "over 20," ">20") shall be excluded from the analysis.

| | | Last Update Date |
|----------------------------------|---|------------------|
| dreamcis ATIGERMED COMPANY | CONFIDENTIAL: THIS DOCUMENT AND THE INFORMATION CONTAINED HEREIN ARE PROPRIETARY TO THE COMPANY AND ARE NOT TO BE DISCLOSED WITHOUT THE WRITTEN PERMISSION OF THE COMPANY. | 02-NOV-2018 |
| STATISTICAL ANALYSIS PLAN (V2.0) | | |

- If only some information of the date used in the continuous data analysis is present and it is therefore not computable, it shall be excluded from the analysis.
- If there is any missing value in the safety data, it shall not be replaced and shall be analyzed as it is.

| dreamcis ATIGERMED COMPANY | | Last Update Date |
|----------------------------------|---|------------------|
| | CONFIDENTIAL: THIS DOCUMENT AND THE INFORMATION CONTAINED HEREIN ARE | |
| | PROPRIETARY TO THE COMPANY AND ARE NOT TO BE DISCLOSED WITHOUT THE WRITTEN PERMISSION OF THE COMPANY. | 02-NOV-2018 |
| STATISTICAL ANALYSIS PLAN (V2.0) | | |

References

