### **9.2.2 Drop-Out Subjects**

Once a subject is dropped out from the study, no further information for that subject will be collected. However, the reason for drop-out will be reported and serious adverse events will be reported to AbbVie until 70 days following the intake of the last dose of adalimumab.

Subjects will be dropped out from the study:

- 1) If the subjects choose to withdraw from the study
- 2) Where ethical or practical conflicts hinder the procedure of the study, and such cases will be determined based on the investigator's judgment
- 3) In case of Adalimumab discontinuation at any point during study period

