## **General Considerations**

Continuous variables will be described with the number of subjects, arithmetic mean and standard deviation. For categorical variables, the frequency and proportion will be presented. The values such as arithmetic mean, standard deviation, and proportion will be

rounded to two decimal places. If the observation value is missing value, it will be treated as a missing value in the analysis.

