### **Baseline Characteristics including demographics**

Descriptive statistics will be used to present variables regarding demographics and disease/medication related data. Continuous variables will be described with the number of subjects, arithmetic mean and standard deviation. For categorical variables, the frequency and proportion will be presented. The values such as arithmetic mean, standard deviation, and proportion will be rounded to two decimal places.

If the observation value is missing value, NRI and LOCF will be used for a missing value. Statistical analyses will be performed using SAS V9.2 or higher.

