6.3 Effectiveness Endpoint Analysis Method

6.3.1 Primary Effectiveness Endpoint

- (1) The frequency and percentage of the subjects who showed a clinical response^a at visit 2 (week 8) will be presented, and the 95% confidence interval will be calculated.
- (2) The frequency and percentage of the subjects who showed a persistent clinical response^a at visit 2 (week 8), visit 4 (week 24), and visit 8 (week 56) will be presented, and the 95% confidence interval will be calculated.

Here, if any item in either the full or partial Mayo score was not collected, the subject will be excluded from this analysis.

^a Clinical response: It is defined as the case with 3 points or more reduction and 30% or more reduction in the full Mayo score at visit 2 (week 8) from visit 1 (baseline) plus 1 point or more reduction in the rectal bleeding subscore or an absolute rectal bleeding subscore of 1 point or less.

^b Persistent clinical response: Defined as the case of 3 points or more reduction and 30% or more reduction in the full Mayo score both at visit 2 (week 8) and visit 8 (week 56) from visit 1 (baseline) plus 1 point or more reduction in the rectal bleeding subscore or absolute rectal bleeding subscore of 1 point or less. At visit 4 (week 24), however, it is defined as the case of 2 points or more reduction and 30% or more reduction in the partial Mayo score plus 1 point or more reduction in the rectal bleeding subscore or an absolute rectal bleeding subscore of 1 point or less.

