6.3.2 Secondary Effectiveness Endpoint

If any item in either the full or partial Mayo score was not collected, the subject will be excluded from the relevant secondary effectiveness endpoint analysis.

(1) Percentage (%) of subjects who showed clinical remission^c at visit 2 (week 8) and who showed clinical remission^c at visit 4 (week 24) and visit 8 (week 56) among those who showed a clinical response at visit 2 (week 8)

CONFIDENTIAL:

THIS DOCUMENT AND THE INFORMATION CONTAINED HEREIN ARE PROPRIETARY TO THE COMPANY AND ARE NOT TO BE DISCLOSED WITHOUT THE WRITTEN PERMISSION OF THE COMPANY.

02-NOV-2018

Last Update Date

STATISTICAL ANALYSIS PLAN (V2.0)

The frequency and percentage of subjects who showed clinical remission^c at visit 2 (week 8) will be presented. Among the subjects who showed a clinical response at visit 2 (week 8), the frequency and percentage of those who showed clinical remission^c at visit 4 (week 24) and visit 8 (week 56) will also be presented.

^c Clinical remission: Defined as the case of full Mayo score ≤2 points and each subscore ≤1 point. For visit 4 (week 24), however, it is defined as the case of partial Mayo score ≤2 points and each subscore ≤1 point.

(2) Percentage (%) of subjects who showed a clinical response at visit 2 (week 8) without steroid administration^d, and who showed a clinical response at visit 4 (week 24) and visit 8 (week 56) without steroid administration^d among those who showed a clinical response at visit 2 (week 8)

The frequency and percentage of subjects who showed a clinical response at visit 2 (week 8) without steroid administration^d will be presented. Among these subjects, the frequency and percentage of those who showed a clinical response at visit 4 (week 24) and visit 8 (week 56) without steroid administration^d will also be presented.

^d Clinical response without steroid administration: Defined as the case where the subject showed a clinical response without using systemic steroids within 12 weeks before he/she was evaluated. For visit 2 (week 8), however, it is defined as the case where the subject showed a clinical response without using systemic steroids within 8 weeks before he/she was evaluated.

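### SAP 6.6 carries partial Mayo scores past an adalimumab stop and is not ranked against the exclusion rule in SAP 6.3, so no SAP rule counts a stop before week 24 as a failure

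*SAP*

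**What the plan says.** **How a missing score arises.** Protocol 9.2.2 and SAP section 3 make adalimumab discontinuation a reason for drop-out. Protocol 9.2.2 adds: "Once a subject is dropped out from the study, no further information for that subject will be collected" (reason for drop-out and serious adverse events apart). A subject who stops before week 24 therefore has no week-24 Mayo score.

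**How week 24 is judged.** SAP 4.1.1 lists week 24 in the primary endpoint. SAP 6.3.1, footnote b, sets its own response rule for that visit: "At visit 4 (week 24), however, it is defined as the case of 2 points or more reduction", and at least 30%, both on the partial Mayo score, with a rectal bleeding condition. SAP 6.3.2, footnote c, likewise defines week-24 remission on the partial score (total at most 2, no item above 1). Neither needs endoscopy.

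**What happens to missing scores.** Several rules stand side by side:

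- SAP 6.6, partial Mayo items for response and remission: "the most recently obtained value shall be analyzed as if it were obtained at the" time in question (LOCF).
- SAP 6.6, endoscopy: "If a missing value occurs at the endoscopic findings subscore in the full Mayo score, it shall not be replaced".
- SAP 6.3.1, primary endpoint: "if any item in either the full or partial Mayo score was not collected, the subject will be excluded from this analysis".
- SAP 6.3.2, secondary endpoints: "the subject will be excluded from the relevant secondary effectiveness endpoint analysis".
- Protocol 9.7, General Considerations: "it will be treated as a missing value in the analysis".
- Protocol 9.7, under the baseline characteristics heading: "NRI and LOCF will be used for a missing value".

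Neither document ranks these rules or says how a subject who stopped treatment is counted at week 24.

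**The concern.** LOCF in SAP 6.6 can complete the week-24 assessment of someone who is no longer treated or followed. The carried value is an on-treatment score from week 8 or week 16, and the week-8 score may be the one that made the subject a responder. Exclusion under SAP 6.3 removes the same subject from the denominator. Either way the week-24 percentage can read as durability among week-8 responders while early stops are absorbed or dropped.

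The week-24 response and remission rates, and their comparison by TNF antagonist naivety in SAP 6.5, depend on which rule the programmer picks. If LOCF is picked, the same stopper can be a success at week 24 and not evaluable at week 56, so the two results describe different populations.

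**Working it through.** **1. The plan's own figure.** The documents give no number for LOCF or for early stops. The only computable design figure is 147 subjects. For a proportion of 75%, a total 95% interval width of 15 points and 5% drop-out, the exact (Clopper-Pearson) interval needs n = 139 (width 0.14999), and 139 / 0.95 = 146.3, rounded up to 147. The figure reproduces. It serves only to size the illustration: 0.75 x 139 = 104 week-8 responders (assumed).

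**2. Can a carried week-8 score meet the week-24 rules?** Scores are listed as stool frequency, rectal bleeding, global assessment, endoscopy.

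- *Carried as a response.* Baseline 2, 2, 2, 2 (full 8, partial 6); week 8 scores 1, 1, 1, 2 (full 5, partial 3). The full score falls 3 points (37.5%) and bleeding falls 1, a week-8 response. The partial score falls 3 points (50%), so the carried score is a week-24 response.
- *Carried as a remission.* Same baseline; week 8 scores 1, 0, 1, 1 (full 3, partial 2). This is a response but not a week-8 remission, because the full score exceeds 2. Carried forward, the partial score of 2 with no item above 1 is a week-24 remission.
- *Carried as a non-response.* Baseline 2, 2, 2, 3 (full 9, partial 6); week 8 scores 2, 1, 2, 1 (full 6, partial 5). The full score falls 3 points (33%) and bleeding falls 1, a week-8 response. The partial score falls only 1 point, so the carried score fails at week 24.

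Enumerating every combination with baseline full Mayo at least 6 and endoscopy at least 2 gives 7,585 baseline/week-8 patterns that meet the week-8 response rule. Carried unchanged, 6,079 (80.1%) meet the week-24 response rule and 1,506 (19.9%) do not. Where no item is worse than baseline, 4,111 of 4,510 (91.2%) meet it. These are unweighted shares of score patterns, not of patients, and concern response only.

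**3. Size against non-responder imputation (NRI).** Let f be the share of week-8 responders who stop before week 24, q the share of stoppers whose carried score responds, and r the response rate among those still observed.

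- LOCF minus NRI = f x q. Ten such stoppers: 10 / 104 = 9.6 points. With f from 5% to 15% and q from 50% to 100% (assumed): 0.05 x 0.50 = 2.5 points to 0.15 x 1.00 = 15 points.
- Exclusion minus NRI = f x r. With 10 stoppers and 75 of 94 observed responding: (10/104) x (75/94) = 7.7 points.

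**4. The three rules together.** Assumed: 104 week-8 responders, r about 80%, counts rounded to whole subjects. The LOCF column shows none / half / all of the carried scores responding.

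| Stop before week 24 | Observed responders | LOCF, % | Exclusion, % | NRI, % |
|---|---|---|---|---|
| 5% (5) | 79/99 | 76.0 / 77.9 / 80.8 | 79.8 | 76.0 |
| 10% (10) | 75/94 | 72.1 / 76.9 / 81.7 | 79.8 | 72.1 |
| 20% (21) | 66/83 | 63.5 / 73.1 / 83.7 | 79.5 | 63.5 |
| 30% (31) | 58/73 | 55.8 / 71.2 / 85.6 | 79.5 | 55.8 |

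LOCF exceeds exclusion only when q is greater than r. With 10% stopping and 8 of 10 carried scores responding, LOCF gives 83/104 = 79.8%, the same as exclusion.

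**5. Week 56.** Response there needs the full Mayo score. SAP 6.6 does not replace a missing endoscopic subscore, so LOCF alone cannot complete it.

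**The case against.** A reader might infer that every week-8 responder who stops before week 24 is scored a week-24 responder. The documents do not support that. First, the exclusion sentence in SAP 6.3.1 is not limited to week 56. Its mention of the partial score fits week 24, the only visit in that section judged on it, and a carried value is arguably not a collected one. On that text the stopper is excluded. Second, even under LOCF the carried score can fail. A stop after week 16 carries the week-16 score, and a subject who stops for inadequate response may carry a poor one.

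The exclusion reading is not decisive either. The reading that gives both rules effect is to impute first and then exclude whoever is still incomplete, chiefly those without endoscopy. If exclusion came first, the LOCF sentence, written expressly for response and remission, would have little left to act on.

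Other limits stand:

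- Upward bias is shown only against NRI. Between LOCF and exclusion the direction is open.
- Protocol support for NRI is thin: it is named once, beside LOCF, under the baseline heading. The case for it here rests on what the week-24 rate is meant to describe.
- The protocol's primary endpoints are weeks 8 and 56. SAP 4.1.1 adds week 24, but SAP 4.1 makes its analysis conditional and for interim results.
- An effect on the steroid-free endpoints is not shown. LOCF covers Mayo items only, and they also need steroid information that is not collected after drop-out.
- The planned 5% drop-out is the only related figure and is not a stop rate before week 24. The 15-point end assumes that every carried score responds.

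**Conclusion.** The concern holds in this form: SAP 6.6 has no exception for treatment stops, and the SAP does not say whether it or the exclusion sentences in 6.3.1 and 6.3.2 prevail. Under LOCF a stopper can become a week-24 success; under exclusion the stopper leaves the denominator; under neither does the stop itself count as a failure. Either rule can therefore overstate week-24 response among all week-8 responders.

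The size cannot be fixed from the documents. The 2.5 to 15 points for LOCF over NRI rest on assumed stop rates, an assumed share of carried scores that respond and, for the 9.6 points per 10 such stoppers, an assumed 104 week-8 responders. The point is confined to results judged on the partial Mayo score and does not reach week-56 response. It should be corrected, but it does not threaten the protocol's primary endpoints.

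**What to change.** Editing SAP 6.6 alone would leave the exclusion sentences in force, so the change needs four parts:

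1. In SAP 6.6, state that Mayo items are not carried forward past adalimumab discontinuation or study drop-out.
2. Count a week-8 responder who stopped or dropped out before week 24 as a week-24 non-responder and non-remitter, with all week-8 responders as the week-24 denominator, as SAP 2.5.1 already does for week 56.
3. State that this overrides the exclusion sentences in SAP 6.3.1 and 6.3.2 for these subjects.
4. Limit LOCF to missed visits in subjects still on treatment, or show it only as a sensitivity analysis.

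The cost is a sentence or two and one programming flag from the discontinuation and drop-out data. The downside is that the reported week-24 rates become somewhat lower. The table above shows how much under the assumed stop rates.

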### **Secondary Endpoints:**

- The percentage of subjects with clinical remission at week 8 and 56 (in week 8 responders)

; The frequency and proportion of subjects with clinical remission at week 8 and 56 will be presented.

- The percentage of subjects with steroid-free remission at week 8 and 56 (in week 8 responders)

; The frequency and proportion of subjects with steroid-free remission at week 8 and 56 will be presented.

- The percentage of subjects with mucosal healing at week 8 and 56 (in week 8 responders)

; The frequency and proportion of subjects with mucosal healing at week 8 and 56 will be presented.

- The change of partial Mayo score from baseline overtime

; The descriptive statistics (the number of patients, mean, standard deviation, min, max) for partial Mayo score according to study visit and the change from baseline overtime will be presented.

- The change of the composition of Fecal micro biota from baseline at week 56
- The mean change of Fecal calprotectin level from baseline at week 56

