2.3.2 Inclusion Criteria

- (1) Subject must be an adult \geq 19 years
- (2) Subject with active moderate-to-severe ulcerative colitis patients with Mayo score of ≥ 6 points and endoscopic sub-score of ≥ 2 points despite treatment with corticosteroids and/or immunosuppressants.
- (3) Subject who must have tuberculosis (TB) Screening Assessment in accordance with Korean reimbursement guideline
- (4) Subjects who are started on adalimumab treatment in normal clinical practice setting by their physician.
- (5) Subject must provide written authorization form to use personal and/or health data prior to the entry into the study

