 (First dose (80/160 mg), second dose (40mg/80mg), dose escalation (yes/no), administration frequency
 (2 times and below / more than 2 times), reason for discontinuation (inadequate response / adverse event / others))
- TNF antagonist naivety (yes/no)
- * The categories can be modified according to the structure and characteristics of the collected data.

^a Onset age: The period from the date of birth to the date of diagnosis

^b Disease duration: The period from the date of diagnosis to the date of consent of the subject

 $^{^{}c}$ Adalimumab trough level: The below the quantification limit (BQL) value of the adalimumab trough level is <0.040 μ g/mL. If collected like this, it is analyzed by replacing it with 0.040 μ g/mL, and the total number of replacements will be specified.

d Antibody adalimumab: The below the quantification limit (BQL) value of antibody adalimumab will be confirmed at the central lab after the final data collection is completed. The data at the BQL will be analyzed by replacing them with the lowest measurable value, and the total number of replacements will be specified.

^e Total administration period: It is calculated as the period from the administration start date to the administration end date, and if administration is ongoing, the administration end date is replaced with the last visit date.

^f Period to dose escalation: The period from the administration start date to the first dose escalation (every 1 week)

| dreamcis ATIGERMED COMPANY | | Last Update Date |
|-------------------------------|--|------------------|
| | CONFIDENTIAL: THIS DOCUMENT AND THE INFORMATION CONTAINED HEREIN ARE | |
| | PROPRIETARY TO THE COMPANY AND ARE NOT TO BE DISCLOSED | 02-NOV-2018 |
| | WITHOUT THE WRITTEN PERMISSION OF THE COMPANY. | |
| STATISTICA | LANALYSIS PLAN (V2 0) | |

^g The classification of the co-morbidities and concomitant medications for UC is presented with the terms classified based on the dictionary specified in the latest version of DMP. Here, the co-morbidities and concomitant medications are summarized with the system organ class (SOC) and preferred term (PT) based on the MedDRA classification. The concomitant medications for UC are summarized with anatomical

h Biologics: Single-dose infliximab or a single dose of another medication is classified as 1 medication, and if infliximab and another medication are both administered, it is classified as 2 medications and above.

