For the rectal bleeding subscore, the descriptive statistics (number of patients, mean, standard deviation, median, 1st quartile, 3rd quartile, minimum, maximum) will be presented at visit 1 (baseline), visit 2 (week 8), and visit 8 (week 56) by dividing the subjects into two groups according to the clinical response at visit 2 (week 8) and visit 8 (week 56). T-test or Wilcoxon rank sum test will be performed to determine if there is a difference in the mean rectal bleeding subscore depending on the clinical response.

In addition, for the difference in the change of the rectal bleeding subscore at visit 2 (week 8) and visit 8 (week 56) from visit 1 (baseline), the descriptive statistics (number of patients, mean, standard deviation, median, 1st quartile, 3rd quartile, minimum, maximum) will be presented for each group. Paired t-test or Wilcoxon signed rank test will be performed to determine if there is a difference in the change within the group at each visit compared to visit 1 (baseline).

(8) Mean change in the fecal calprotectin level^a at visit 2 (week 8) and visit 8 (week 56) from visit 1 (baseline)

For the fecal calprotectin level^a, the descriptive statistics (number of patients, mean, standard deviation, median, 1st quartile, 3rd quartile, minimum, maximum) will be presented at each visit for the following subgroups. T-test or Wilcoxon rank sum test will be performed to determine if there is a difference between the groups within each subgroup.

- Depending on the clinical response at visit 2 (week 8)
- Depending on the clinical response at visit 8 (week 56)
- Depending on the clinical remission at visit 2 (week 8)
- Depending on the clinical remission at visit 8 (week 56)
- Depending on the mucosal healing at visit 2 (week 8)
- Depending on the mucosal healing at visit 8 (week 56)

^a Fecal calprotectin level: The below the quantification limit (BQL) value of the fecal calprotectin level is <39.000 mg/kg, and when collected like this, it will be analyzed by replacing it with 39.000 mg/kg, and the total number of replacements will be specified.

| | | Last Update Date |
|----------------------------------|---|------------------|
| dreamcis ATIGERMED COMPANY | CONFIDENTIAL: THIS DOCUMENT AND THE INFORMATION CONTAINED HEREIN ARE PROPRIETARY TO THE COMPANY AND ARE NOT TO BE DISCLOSED. | 02-NOV-2018 |
| | WITHOUT THE WRITTEN PERMISSION OF THE COMPANY. | 02 1.0 . 2010 |
| STATISTICAL ANALYSIS PLAN (V2.0) | | |

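### SAP 6.6 deletes laboratory values recorded as above a limit; if calprotectin has such values, the planned group comparisons are weakened and the mean change is distorted in an uncertain direction

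*SAP*

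**What the plan says.** SAP 6.6 opens with "If there are any missing or incomplete data, they shall be handled as shown below". For continuous data it then rules that "the data that include a sign of inequality, symbols, etc. (e.g., 'over 20,' '>20') shall be excluded from the analysis". Both of its examples are above-limit entries, and it asks for no count of what is excluded.

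For calprotectin, footnote a of SAP 6.3.2(8) handles results below 39.000 mg/kg: "when collected like this, it will be analyzed by replacing it with 39.000 mg/kg", with the number of replacements stated. The two footnotes in SAP 6.2 are also lower-end rules with a count. Trough level: "If collected like this, it is analyzed by replacing it with 0.040". Antibody: "The data at the BQL will be analyzed by replacing them with the lowest measurable value". Neither document has an upper-end rule for any assay. Protocol 9.7 speaks only of missing values.

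The protocol lists as a secondary endpoint "The mean change of Fecal calprotectin level from baseline at week 56". SAP 6.3.2(8) describes calprotectin at each visit by response, remission and mucosal healing at weeks 8 and 56: "T-test or Wilcoxon rank sum test will be performed to determine if there is a difference between the groups within each subgroup". SAP 6.5 uses calprotectin as a predictor, as a below-250 outcome and as a below-250 percentage by visit.

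**The concern.** A result reported as above a limit is known to be at least that large. Treating it as missing selects on the outcome: the highest subjects leave the analysis because they are high. At the lower end the SAP does the opposite and keeps the subject, substitutes the limit and counts.

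Loss of high values need not be balanced. Entry requires active disease (SAP 2.3.2: "Subject with active moderate-to-severe ulcerative colitis patients with Mayo score of" at least 6), so above-limit results are most likely at baseline. At any one visit they are most likely in the group doing worse. The first imbalance bears on the change from baseline. The second bears on the between-group comparisons, where the groups are pulled together.

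**Working it through.** The plan gives no figure on this point, so this is a check of direction and range. Every calprotectin input is an assumption. Values are lognormal with median m and log-SD s, and U is the assumed upper limit.

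**1. Group comparison at baseline by week-8 response.** Group sizes come from SAP 2.4: 147 × 0.95 ≈ 140, and 75% response gives 105 and 35. Assumed medians are 900 in responders and 1400 in non-responders, with s = 1 in both groups.

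With a = ln(U/m)/s:
- share above U = 1 − Φ(a)
- median after deletion = m·exp(s·Φ⁻¹(Φ(a)/2))
- mean after deletion = m·exp(s²/2)·Φ(a − s)/Φ(a)
- mean after substitution = m·exp(s²/2)·Φ(a − s) + U·(1 − Φ(a))

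At U = 1800, a = ln(1800/900) = 0.693 and ln(1800/1400) = 0.251, so 24.4% and 40.1% lie above the limit. The medians after deletion are 660 and 828, a difference of 168 against the true 1400 − 900 = 500. Substitution leaves both medians unchanged, since both lie below U. Power is for the rank-sum test at two-sided 0.05, from 20,000 simulated trials per limit.

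| | Full data | U = 1800 | U = 3000 | U = 6000 |
|---|---|---|---|---|
| Above U, responders / non-responders | – | 24.4 / 40.1% | 11.4 / 22.3% | 2.9 / 7.3% |
| Median difference, deleted | 500 | 168 | 275 | 410 |
| Median difference, substituted | 500 | 500 | 500 | 500 |
| Mean difference, deleted | 824 | 130 | 233 | 436 |
| Mean difference, substituted | 824 | 243 | 401 | 613 |
| Power, deleted | 59.0–60.1% | 21.6% | 33.6% | 48.6% |
| Power, substituted | 59.0–60.1% | 56.5% | 58.1% | 59.3% |

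Repeat runs at 1800 gave about 59% with full data, 20–23% deleted and 55–57% substituted.

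A wider grid looked at follow-up contrasts. It took a baseline median of 1500, falls of 2 to 8 fold in responders and 1 to 2 fold in non-responders, baseline log-SD 0.9 or 1.2, follow-up log-SD 0.9 to 1.5, correlation 0 to 0.6, and limits 0.67 to 4 times the baseline median. Deletion shrank the group contrast in 576 of 576 scenarios at 75% response and in 576 of 576 at 50%. Both groups shared one log-SD within each scenario.

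**2. Mean change from baseline.** Deletion keeps pairs with both values at or below U. Correlation is 0.4. True change = m₁·exp(s₁²/2) − m₀·exp(s₀²/2).

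| Medians, baseline → follow-up | Log-SD, baseline / follow-up | U | Above U, baseline / follow-up | True | Deleted | Substituted |
|---|---|---|---|---|---|---|
| 1000 → 200 | 1.0 / 1.0 | 1800 | 27.8 / 1.4% | −1319 | −527 | −745 |
| 1000 → 300 | 0.8 / 1.5 | 1800 | 23.1 / 11.6% | −453 | −475 | −509 |
| 1000 → 400 | 1.0 / 1.5 | 3000 | 13.6 / 9.0% | −417 | −450 | −489 |
| 1000 → 300 (75%) or 1000 (25%) | 0.8 / 1.3 | 1800 | 23.1 / 14.4% | −271 | −407 | −415 |

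In the first row deletion understates the fall. In the other three it overstates it, although above-limit values still lie mainly at baseline, and substitution is further off than deletion. In the grid, deletion shrank the mean fall in 213 of 216 week-56 scenarios restricted to responders (falls of 3 to 10 fold). At week 8 it did so in 504 of 552 scenarios at 75% response and 440 of 504 at 50%.

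**3. Share below 250, if 6.6 is applied in 6.5(2).** For any U of at least 250, every deleted subject is above 250. The share p becomes p/(1 − q), where q is the share above U, so it can only rise.
- Baseline median 1000, log-SD 1: p = Φ(ln 0.25) = 8.3% becomes 11.5 / 9.6 / 8.6% at U = 1800 / 3000 / 6000.
- Follow-up median 200, log-SD 1: 58.8% rises by less than 1 point.
- Follow-up medians 200 (75% of subjects) and 1000 (25%), log-SD 1.3, U = 1800: 46% becomes 52%.

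**The case against.** The strongest objection is that the trigger is not shown. No upper limit is stated, no above-limit record appears, and the examples in 6.6 are generic and tied to no assay. Where the SAP knows an assay limit it writes a replacement rule. That stands: the size cannot be fixed from the documents, and the point is conditional.

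Second, a reader might infer that deletion always makes the fall look smaller, because high values belong to baseline. The documents do not support this. Nothing in them fixes the spread at follow-up, and week 8 still includes non-responders. With a wider follow-up spread, deletion also removes the subjects who worsened, and the fall can be overstated.

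Third, SAP 6.3.2(8) is headed as a mean change, but its text specifies only levels at each visit and group tests, unlike items (5) to (7), which add change summaries and paired tests. The pairwise deletion in step 2 is therefore an assumption. This is another reason to rest the point on the group comparisons, which are specified.

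A reader might also infer that 6.6 overrides the below-limit footnotes and deletes results such as those below 39.000. Its wording reaches them, but the footnotes are variable-specific and require counts, so they are best read as prevailing. Only a sentence saying so is missing. No bias is claimed for CRP or ESR: 6.6 is their only rule for signed values, but neither size nor direction is established.

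**Conclusion.** The concern holds for the group comparisons. If calprotectin values above a reporting limit occur, 6.6 deletes them because they are high, shrinks the planned contrasts and costs rank-test power. In the illustration at a limit of 1800 power drops from about 59% to 20–23%, and substitution keeps 55–57%. This rests on assumed lognormal values with equal log-SD in both groups; the loss is smaller at higher limits and nil if no such values exist.

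For the mean change the supportable statement is weaker: it can be distorted, probably towards a smaller fall at week 56 in responders, with no certain direction. The below-250 share rises if 6.6 is applied there. The primary Mayo-based endpoint is unaffected. Importance is minor to moderate; the bullet should be changed, with medium confidence because the trigger is unverified.

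**What to change.** First ask the laboratories which signed values occur and what the reporting limits are. If there are none, the cost is one query. Otherwise replace the 6.6 bullet with:

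> A laboratory value recorded with an inequality sign takes its reporting limit, and the number replaced is reported by variable, visit and end (lower or upper). The below-limit rules in 6.2 footnotes c and d and 6.3.2(8) footnote a prevail. Entries from which no numeric limit can be recovered are excluded and counted.

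In 6.5(2) and (3), classify a signed value directly against 250 or 5 mg/L when its limit decides the category. Put CRP in one unit first: 6.2 lists mg/dl, and 5 mg/L is 0.5 mg/dl.

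Where values were replaced, use the medians and the rank-sum test, both already in the SAP, for the calprotectin group comparisons. Say that means and mean changes are affected by censoring, without stating a direction.

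The cost is one bullet, one derivation step and short additions to 6.3.2(8) and 6.5, with no new data. The downside is that substitution adds ties, which cost little power here, and does not remove bias in the mean change. When the follow-up spread is wider than at baseline, it can be further from the truth than deletion.
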